6 STUDY PROCEDURES

6.1 Summary of Procedures

Table 6-1: Schedule of Study Procedures

Time (Day)*	Screen/ Baseline	Treatment phase							
	0 ¹ Visit #00/ Visit #01 ⁸	30 (±5 days) Visit #02	60 (± 5 days) Visit #03	90 (± 5 days) Phone contact Visit #04	120 (± 5 days) Visit #05	150 (± 5 days) Phone contact Visit #06	180 (± 5 days) Visit #07	Day 7 (+ 5 days) Phone contact post 180 day study period or early withdrawal Visit #08	Day 270 (± 5 days) Phone contact Confirm ongoing therapy Visit #09
Informed consent	X								
Demographics	X								
Randomization	X								
Vitals: HR, BP ¹⁰	X ⁸	X	X		X		X		
Physical Exam of lesion ²	X	X	X		X		X		
Photograph of lesion	X	X	X		X		X		
Medical History	X								
Physical Exam (systems assessment) ⁹	X	X	X		X		X		
Actual Weight	X	X	X		X		X		
Study Drug Dispensation	X	X	X		X				
Review of Participant Diary (Treatment Administration Info)	X	X	X		X		X		
SOC Timolol Dosing Info (from Phone Script/Follow-up Diary)								X	X
Concomitant Medications	X	X	X	X	X	X	X	X	
Adverse Events	X ^{4,8}	X	X	X	X	X	X	X	X ³
Blood sampling ⁵	X	X	X		X		X		
Parent reported QOL Survey ⁷	X		X				X		
Hemangioma Dynamic Complication Scale ⁶	X	X	X		X		X		
Assessment for treatment failure		X	X		X		X		

¹ Refers to time point prior to start of study drug and may be the same calendar date as day 1.

² This includes treating physician's assessment by Visual Analog Scale (VAS) and measure of width and

thickness. Note: VAS should only be performed at visits 02, 03, 05, 07 and unmasking.

³AEs of special interest will include bradycardia, hypotension, new alteration in mental status, new local skin irritation, new sleep disturbance, apnea, bronchospasm, hypoglycemia, and diarrhea.

⁴AEs will be collected following initial study-specific procedure (e.g., screening, blood draws, dosing)

⁵For infants who are enrolled into the PK portion of the study; up to 3 samples will be obtained throughout the study period and at least one sample should be collected within 2 hours of dosing. Clinic visits for infants in the PK portion of the study will be scheduled to fall within the appropriate time period. Blood pressure and heart rate must be collected within 15 minutes before or after sample collection.

⁶The Hemangioma Dynamic Complication Scale must be collected for all participants.

⁷The parent-reported QOL survey is not required for non-English speaking parents.

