6.3 Enrollment/Baseline

Research staff will obtain informed consent from the parent/guardian for all participants who satisfy eligibility criteria.

Once the informed consent has been obtained the following information will be recorded in the CRF:

1. Infant demographics, including birth weight and gestational age at birth and postnatal age.
2. Medical history (birth history and cardiac or pulmonary diagnoses)
3. Physical examination, including weight, height/length, baseline blood pressure, heart rate. Note, at the Baseline Visit, blood pressure* and heart rate must be at 1 hour and 2 hours after the first application of timolol.
4. Photographs and measurements of the IH. Collection of data on the clinical characteristics and measurement of width and thickness of the target hemangioma.
5. Adverse events following initial study-specific procedure (see Table 6-1)
6. Hemangioma Dynamic Complication Scale
7. Parental Hemangioma Quality of Life (QoL) screen
8. Concomitant Medications

* The preferred method of blood pressure collection is auscultation (i.e. manual), however, blood pressure may be collected via machine. Whichever method is used at visit #01 (baseline) should be used at all subsequent visits. Blood pressure measurements should include systolic and diastolic pressure measurements.

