4. Absolute change in hemangioma dynamic complication scale from Day 0 to end of study within each treatment arm.
5. Assess time to partial response by comparing baseline to day 30, day 60, day 120 and day 180 in both treatment arms.
6. Absolute change in IH-QoL score scale from Day 0 to end of study within each treatment arm.

Secondary **safety** endpoints are the rate of serious adverse events and adverse events of special interest (Section 8.1.2) from randomization to Day 180 in infants treated with topical timolol maleate (0.25% and 0.5%) GFS for the treatment of infantile hemangioma.

Exploratory Endpoints:

Exploratory PK endpoints include estimation of PK parameters such as clearance (CL), volume of distribution (V), area under the curve (AUC), and maximum concentration (C_{max}), as possible.

The relationship between different hemangioma characteristics and plasma concentrations may also be described as an exploratory endpoint.

Treatment Failure for Partial Response in Hemangioma Color or Volume

The infant will be considered a treatment failure for the primary endpoint of partial response of VAS-volume or the secondary endpoint of partial response of VAS-color from baseline to Day 180 if any of the following conditions are met:

1. Partial response not achieved at the Day 180 visit in infants who complete the 180-day treatment period.
2. Infant withdrawn from masked treatment due to progressive disease. This will include participants randomized to the 0.25% treatment arm and switched to the 0.5% treatment arm.
3. Ulceration of the target hemangioma after initiation of masked treatment.
4. Infant withdrawn from study treatment due to safety concerns.
5. Study drop-out or loss to follow-up after the 30-day visit and before the 180-day visit for reasons other than progressive disease, ulceration, or safety concerns without having achieved partial response at the last study visit before drop-out.

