10.4.4 Efficacy Analysis

Key efficacy endpoints are summarized in Section 10.1. Chi-square or Fisher's exact tests will be used to test response proportion hypotheses at study end. Response proportions will be further compared via odds ratio, difference in proportion, and confidence interval estimates.

Further adjusted analyses taking into account postnatal age, gestational age, and other baseline or demographic covariates of interest via logistic regression will be performed. Differences between studies used for the control data will be assessed.

As discussed in Section 10.1, randomized participants who switch to unmasked treatment with timolol maleate 0.5% GFS due to disease progression will be classified as treatment failures in the primary analysis. VAS scores following the switch to unmasked treatment will be analyzed as a secondary analysis. Both the VAS assessment of change from study baseline and change in VAS score from the time of treatment switching will be summarized in this secondary analysis. The duration of unmasked treatment will be summarized. Partial response of color or volume from the start of randomized treatment will be evaluated in participants who switch treatment using data collected after the treatment switch.

Additional secondary efficacy variables for analysis between randomized treatment arms include severity of the hemangioma, time to partial response, and quality of life measurement variables. Absolute change in overall severity will be measured via hemangioma dynamic complication scale from baseline to Day 180 within each treatment arm. Absolute change in quality of life will be measured via IH-QoL score scale from baseline to Day 180 within each treatment arm. Linear mixed effects modeling techniques will be used to analyze changes in the quantitative VAS scores, severity scale, or quality over time, and adjustments for demographic covariates of interest will be considered.

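### The between-arm IH-QoL analysis does not say how the collected baseline score enters the model; leaving it out would cost precision, by an amount that depends on assumptions the documents do not give

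*Combined protocol and SAP*

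**What the plan says.** The endpoint list in section 10.1 defines the quality-of-life endpoint within arm: "Absolute change in IH-QoL score scale from Day 0 to end of study within each treatment arm". Section 10.4.4 goes further and plans a comparison of arms: "Additional secondary efficacy variables for analysis between randomized treatment arms include severity of the hemangioma, time to partial response, and quality of life measurement variables". It then returns to the within-arm measure: "Absolute change in quality of life will be measured via IH-QoL score scale from baseline to Day 180 within each treatment arm".

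The model for these outcomes is given in one sentence: "Linear mixed effects modeling techniques will be used to analyze changes in the quantitative VAS scores, severity scale, or quality over time", to which the section adds that "adjustments for demographic covariates of interest will be considered". The same section is broader for the binary response: "Further adjusted analyses taking into account postnatal age, gestational age, and other baseline or demographic covariates of interest via logistic regression will be performed". Baseline covariates are named there but not in the mixed-model sentence.

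The baseline score will exist. Section 6.3 lists the "Parental Hemangioma Quality of Life (QoL) screen" among the enrollment data, and the row "Parent reported QOL Survey" in Table 6-1 is marked at baseline, Day 60 and Day 180. A footnote to that table does not require the survey from parents who do not speak English, so the number analysed may be below the number evaluable for the primary endpoint.

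**The concern.** For a continuous score measured before and after randomization, the baseline value is usually the strongest predictor of the later value. Subtracting it is not the same as adjusting for it. Subtraction forces a slope of 1 on baseline, and when the true slope is rho < 1 this adds noise and over-corrects for any chance difference between arms at the start. The arm that starts worse by chance then appears to improve more.

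Nothing in the design balances baseline IH-QoL: section 5.3.2 stratifies by site and age group only. The single mixed-model sentence covers VAS, the severity scale and quality of life together. VAS is itself a rating of change and has no baseline value to adjust for. IH-QoL does have one, and the shared sentence does not deal with it. What is at stake is the precision of the 0.25% versus 0.5% quality-of-life comparison, and a modelling choice that could be settled after the data are seen.

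**Working it through.** **The plan's own figures.** No power is stated for IH-QoL. The only stated powers, in section 10.3, are 93% and 85% for the two primary comparisons with control. With 35 controls at 0.15, 45 treated, and the normal approximation with pooled null variance at one-sided 0.025 (0.05 halved by Bonferroni), the results are 92.8% at a response of 0.50 and 83.8% at 0.45. Both are within 2 points of the stated figures. This confirms 45 per arm as the planning number and says nothing about quality of life.

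**Inputs**
- From the documents: 45 evaluable infants per arm (10.3) and alpha 0.05 (10.2), taken here as two-sided for a comparison of arms.
- Assumed: correlation rho between baseline and Day 180 IH-QoL of 0.3 to 0.7; true difference between arms of 0.1 to 0.5 SD; equal SDs at the two visits.

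**Variance per infant, in units of the squared SD**
- Change score, unadjusted: 2(1-rho).
- Baseline-adjusted: 1-rho².
- Ratio, change score to adjusted: 2(1-rho)/[(1-rho)(1+rho)] = 2/(1+rho).

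| rho | change score | adjusted | ratio |
|---|---|---|---|
| 0.3 | 1.40 | 0.91 | 1.54 |
| 0.5 | 1.00 | 0.75 | 1.33 |
| 0.7 | 0.60 | 0.51 | 1.18 |

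**Which mixed model falls where.** Generalized least squares with three visits and compound symmetry gives these variances for the Day 180 contrast:
- Baseline as a response with one common mean: 0.91, 0.75 and 0.51, the same as the adjusted analysis, so nothing is lost.
- Baseline as a response with separate arm means: 1.40, 1.00 and 0.60, the same as the change score, so the full loss applies.

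The wording of 10.4.4 permits either.

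**Power.** Two-sample t test, 45 per arm, SD equal to the square root of the variance above. Each cell shows change score, then adjusted, with the points lost in brackets.

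| Difference | rho 0.3 | rho 0.5 | rho 0.7 |
|---|---|---|---|
| 0.1 SD | 6.8% / 7.8% (1.0) | 7.6% / 8.4% (0.9) | 9.3% / 10.1% (0.8) |
| 0.2 SD | 12.5% / 16.6% (4.2) | 15.5% / 19.2% (3.6) | 22.8% / 26.0% (3.2) |
| 0.3 SD | 22.1% / 31.4% (9.3) | 29.1% / 36.9% (7.8) | 44.3% / 50.4% (6.1) |
| 0.5 SD | 50.9% / 69.1% (18.2) | 65.0% / 77.3% (12.3) | 85.7% / 90.7% (5.0) |

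At 0.5 SD and rho 0.8 the loss is about 1.5 points. With 35 per arm (assumed, to allow for families not surveyed), 0.5 SD and rho 0.5, power goes from 54.1% to 66.3%.

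**Chance imbalance.** A baseline difference d moves the change-score estimate by (1-rho)d in magnitude. With 45 per arm, d has standard deviation sqrt(2/45) = 0.21 SD. A difference of 0.2 SD or more in either direction therefore occurs about one time in three (0.2/0.21 = 0.95 standard errors, two-sided probability 0.34). At rho 0.5 such a difference shifts the estimate by 0.5 × 0.2 = 0.1 SD.

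**The case against.** The strongest reply is that silence is not a decision. A reader might infer from 10.4.4 that the baseline score is deliberately left out. The text does not support that: it does not specify how baseline enters the mixed model, and one standard form, with a common baseline mean, already has full efficiency. The covariate clause is permissive, and even demographic adjustment is only to be considered. This stands, and the loss is therefore conditional on the model eventually chosen. It does not remove the point, because the plan equally permits the inefficient forms.

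The second reply is that no planned power is at risk. Section 10.1 defines the endpoint within arm, section 10.2 states hypotheses only for response proportions, and section 10.3 powers only the comparisons with control. This also stands, and it limits the importance of the point. Section 10.4.4 nevertheless plans the between-arm analysis.

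The third concerns size. A reader might take 5 to 18 points as the cost outright. That range needs a 0.5 SD difference between two strengths of the same drug, which nothing in the documents supports. The only between-arm difference they assume, 0.45 against 0.50 response, is an arcsine effect size (Cohen's h) of about 0.10. It concerns another outcome and so does not settle the matter, but at 0.1 SD the loss is only about 1 point.

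Finally, a reader might infer that the unadjusted estimate is biased. Under 1:1 randomization it is unbiased on average; the shift is conditional on the imbalance that happens to occur.

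**Conclusion.** The point holds as a gap in specification with an available gain in precision. Section 10.4.4 plans a between-arm analysis of change in IH-QoL, mentions only demographic covariates for it, and does not say that the collected baseline score is used. If the score is not used, or is modelled as a response with separate arm means, the variance is larger by 2/(1+rho): 18% to 54% larger for rho 0.7 down to 0.3. The resulting power loss runs from about 1 to about 18 points over differences of 0.1 to 0.5 SD with 45 per arm; both the correlation and the difference are assumptions. The importance is low: this is a secondary analysis with no stated hypothesis or power, and neither the primary result nor the within-arm quality-of-life summary is affected.

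**What to change.** In 10.4.4, state that the between-arm IH-QoL model takes the Day 60 and Day 180 scores as outcomes with the baseline IH-QoL score as a covariate, or that it uses all three visits with the arm means constrained to be equal at baseline. Keep within-arm absolute change from baseline to Day 180 as the descriptive summary, so that the endpoint in 10.1 is unchanged. The cost is one sentence, no new data and at most one degree of freedom.

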10.4.5 PK Analysis

If possible, PK parameters will be estimated by the population PK approach using non-linear mixed effects modeling in NONMEM. The relationship between hemangioma characteristics (e.g. hemangioma thickness, timolol formulation, sex, application site, hemangioma surface area, ulceration, or occlusion) and study drug concentration will be estimated. Timolol data from the Pharmacokinetics of Understudied Drugs Administered to Children per Standard of Care study (PTN POP01) will be combined with the data obtained from this study for the exploratory PK analysis.

10.4.6 Safety Analysis

The number and percent of AEs and SAEs will be summarized overall and by each Medical Dictionary for Regulatory Activities (MedDRA) system organ class and preferred term. Prior and concomitant medications will be summarized by World Health Organization (WHO) drug class. Summary statistics for proportion of infants with AEs of special interest will be presented. The equality of AE and SAE event rates will be tested between treatment arms as an exploratory analysis.

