10.2 Study Hypotheses Tested

For the primary analyses of treatment efficacy, let p_{RC} be the proportion with partial or greater response in hemangioma volume for the control cohort, p_{R25} the proportion with partial or greater response in hemangioma volume for the 0.25% arm, and p_{R50} the proportion with partial or greater response in hemangioma volume for the 0.5% arm. The following set of hypotheses will be assessed:

Hypothesis 1 (H_1): The partial response proportion in the 0.5% arm is greater than the partial response proportion in the control cohort.

Null hypothesis H_{10} : $p_{R50} \leq p_{RC}$

Alternative hypothesis H_{1A} : $p_{R50} > p_{RC}$

Hypothesis 2 (H_2): The partial response proportion in the 0.25% arm is greater than the partial response proportion in the control cohort.

Null hypothesis H_{20} : $p_{R25} \leq p_{RC}$

Alternative hypothesis H_{2A} : $p_{R25} > p_{RC}$

A secondary efficacy hypothesis comparing treatment arms will also be tested:

Secondary efficacy hypothesis (H_3): The partial response proportion in the 0.25% arm is not equal to the partial response proportion in the 0.5% arm.

Null hypothesis H_{30} : $p_{R25} = p_{R50}$

Alternative hypothesis H_{3A} : $p_{R25} \neq p_{R50}$

The $\alpha=0.05$ level will be used for hypothesis testing. Hypotheses will be tested with chi-square or Fisher's exact tests. A Bonferroni multiplicity correction will be applied to the α level for the primary hypotheses. Response proportions will be further compared between groups using the odds ratio or estimated differences in proportions and corresponding confidence interval estimates.

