10.3 Sample Size Considerations

Sample size calculations for primary efficacy hypotheses assume that 35 participants will have evaluable data in the untreated control cohort. The following success rates are assumed: 0.15 response proportion in the control cohort, 0.45 response proportion in the 0.25% arm, and 0.50 response proportion in the 0.5% arm. With 45 participants in each treatment arm and $\alpha = 0.05$ as in Section 10.2, this gives the efficacy hypothesis comparing the 0.5% and control arms a power of 93% and the efficacy hypothesis comparing the 0.25% and control arms a power of 85% after applying the Bonferroni multiplicity correction to the alpha level. The study sample size of 100 randomized participants was determined by assuming that up to 10% of randomized infants will drop out with unevaluable partial response.

Sample size calculations for the secondary safety analyses assume that approximately 20% of participants will experience an AE of special interest and 5% will experience an SAE of special interest.^{24,32} With 100 participants across the two treatment groups, 95% Wilson score confidence intervals are (0.02,0.11) (confidence interval width=0.09) for SAEs and (0.13,0.29) (confidence interval width=0.16) for AEs. These intervals are thought to be sufficiently precise for the estimation of key event rates. The probability is 0.63 and 0.99 that at least one event will be seen in the study population for rare events with probabilities 0.01 and 0.05, respectively, of occurring.

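### Safety of the two strengths is compared only by an exploratory equality test; an estimated difference with a 95% interval should replace it

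*Combined protocol and SAP*

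**What the plan says.** The secondary safety endpoints in section 10.1 "are the rate of serious adverse events and adverse events of special interest (Section 8.1.2) from randomization to Day 180" in treated infants. Section 10.4.6 plans counts and percentages of AEs and SAEs by MedDRA class and term. For AESIs it says: "Summary statistics for proportion of infants with AEs of special interest will be presented". Its only between-arm element is the sentence "The equality of AE and SAE event rates will be tested between treatment arms as an exploratory analysis". It names no test, alpha level, effect measure or interval.

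Section 10.3 justifies the safety sample by precision, assuming that "approximately 20% of participants will experience an AE of special interest and 5% will experience an SAE of special interest". It continues: "With 100 participants across the two treatment groups, 95% Wilson score confidence intervals are (0.02,0.11) (confidence interval width=0.09) for SAEs". These intervals describe one rate across both arms.

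For efficacy the plan goes further. Section 10.2 states: "Response proportions will be further compared between groups using the odds ratio or estimated differences in proportions and corresponding confidence interval estimates". Section 10.4.4 repeats this. Both sentences are confined to response proportions.

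**The concern.** Section 2.3.2 names characterising the safety of the two strengths as a benefit of the study, and section 2.1 says that the results may go to the FDA for labelling. The 0.25% versus 0.5% contrast is also the only randomised comparison in the trial, since the controls come from other studies or from families who declined treatment.

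An equality test returns a p-value. It does not say how large a difference the data suggest or what excess they leave open. With few events per arm, the p-value will often be non-significant whether or not the strengths differ. A reader given only that result has no measure of what the trial could rule out, and the pooled intervals in section 10.3 do not supply one.

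**Working it through.** **Inputs from the documents.** There are 100 randomised infants (section 10.3) allocated 1:1 (section 4.1), so about 50 per arm. The safety population is all dosed infants (section 10.4.1). The assumed rates are 20% for AESIs and 5% for SAEs of special interest, stated across participants and not per arm (section 10.3).

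**Assumptions, because the documents are silent.** The safety test is chi-square or Fisher's exact at two-sided alpha 0.05. Section 10.2 names these tests and the 0.05 level for the efficacy hypotheses. The 5% rate is used for SAEs in general. The true difference is taken as a doubling.

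**Step 1: reproduce the plan's safety figures.** The Wilson interval has centre (p + z²/2n)/(1 + z²/n) and half-width z√[p(1−p)/n + z²/4n²]/(1 + z²/n), with z = 1.96 and n = 100.
- p = 0.05: 0.0667 ± 0.0451, or 0.022 to 0.112. The plan gives (0.02, 0.11).
- p = 0.20: 0.2111 ± 0.0777, or 0.133 to 0.289. The plan gives (0.13, 0.29).
- At least one event, 1 − (1 − p)^100: 0.634 at 1% and 0.994 at 5%. The plan gives 0.63 and 0.99.

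All agree. They are pooled figures.

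**Step 2: power of the SAE test.** Power is the sum, over all pairs (x₁, x₂), of Bin(x₁; 50, p₁) × Bin(x₂; 50, p₂) for the pairs with p ≤ 0.05. If 5% is the average over both arms and one arm has twice the risk of the other, then (p + 2p)/2 = 5%, which gives 3.3% and 6.7%.

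| SAE rates | Power, chi-square | Power, Fisher | Missed |
|---|---|---|---|
| 5% vs 10% | 14.5% | 6.3% | 86% to 94% |
| 3.3% vs 6.7% | 10.1% | 2.7% | 90% to 97% |

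By the normal approximation, 80% power for 5% vs 10% needs about 435 infants per arm.

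**Step 3: power of the any-AE test.** The documents give no any-AE rate, so a range of base rates is assumed.

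| Any-AE rates | Power, chi-square | Power, Fisher |
|---|---|---|
| 25% vs 50% | 75% | 67% |
| 30% vs 60% | 88% | 83% |
| 40% vs 80% | 99% | 98% |

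The low power in step 2 is therefore a feature of uncommon events, not of every test in section 10.4.6.

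**Step 4: what an interval would show.** For a difference d = p₁ − p₂ with Wilson limits (l, u) in each arm, the Newcombe limits are d − √[(p₁−l₁)² + (u₂−p₂)²] and d + √[(u₁−p₁)² + (p₂−l₂)²].
- 10/50 vs 10/50: each Wilson interval is 0.112 to 0.330. The half-width is √(0.0876² + 0.1304²) = 0.157, about 16 points.
- 3/50 vs 2/50: +2 points, −8.2 to +12.6, Fisher p = 1.0.
- 5/50 vs 1/50: +8 points, −2.2 to +19.5, Fisher p = 0.20.

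In the last two cases the p-value alone looks unremarkable, while the data remain compatible with an excess of roughly 13 to 20 points.

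**The case against.** The strongest reply is that the plan claims nothing it cannot deliver. The safety objective in section 3 is descriptive, section 10.2 contains no safety hypothesis, and section 10.4.6 labels the test exploratory. Low power for rare events is expected in a phase 2 study of this size. Section 10.4.2 plans proportions by group for discrete variables, so arm-level event percentages are arguably covered already, and a reader could compute an interval from them.

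Most of this stands, and it limits the point in three ways.
- A reader might infer that the trial will declare the strengths equally safe when p exceeds 0.05. No sentence says so. This is a risk of misreading, not a planned conclusion.
- A reader might infer that every planned safety comparison is hopelessly underpowered. Step 3 shows that this does not follow for any AE. AESIs are not named in the equality test, so power figures for AESIs would describe a test that is not planned.
- A reader might infer that safety has no intervals at all. Section 10.3 frames the pooled rates with Wilson intervals; what is missing is an interval for the difference.

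The reply does not meet the remaining gap. A descriptive objective calls for an estimate, and a test of equality with no effect size does not describe the difference. The exploratory label excuses low power but is no reason to omit the interval, which the plan already provides for efficacy.

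**Conclusion.** The point holds as a minor one, a cheap improvement. The only formal comparison of safety between strengths is a test that gives no estimate, and for SAEs a non-significant result would carry little information. The miss rate for a doubling is 86% to 94% if 5% is the lower arm's rate, and 90% to 97% if 5% is the average over both arms, which is closer to how section 10.3 words it. These figures rest on 50 infants per arm, two-sided alpha 0.05, a doubling as the true difference, and the use for all SAEs of a rate stated for SAEs of special interest. Nothing in the plan is misstated, and its own safety figures reproduce.

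**What to change.** In section 10.4.6, replace the equality-test sentence with text to this effect:

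- For each of SAE, AESI and any AE, give the proportion of infants with at least one event by randomised arm, with a 95% Wilson interval.
- Give the difference, 0.5% minus 0.25%, with a 95% Newcombe interval.
- In the main comparison, count events up to any switch to open-label 0.5%. Show post-switch events separately, or in a sensitivity analysis by strength received. Sections 4.1 and 5.3.6 move progressing infants from 0.25% to open-label 0.5%, and section 10.4.1 does not say how they are grouped for safety. Cutting at the switch shortens follow-up for those infants, so days at risk should be reported by arm.
- Keep any p-value as supplementary, and state that non-significance is not evidence of equal safety.

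In section 10.3, add that the between-arm 95% half-width is about 16 points at a 20% rate.

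The cost is a few sentences and one more table column, with no new infants or data. The small downside is that the estimate of the difference between strengths will look visibly imprecise.
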